### 5.3. Dulaglutide (LY2189265)

Dulaglutide, which contains two analogs of the endogenous hormone GLP-1, is administered as a once-weekly subcutaneous injection to improve glycemic control in patients with type 2 diabetes mellitus. Dulaglutide has received regulatory approval in some countries and is under review in other countries.

The biosynthetic dulaglutide molecule, produced using mammalian cell culture, consists of 2 identical disulfide-linked chains, each containing an N-terminal GLP-1 receptor agonist sequence covalently linked to a human IgG4 heavy chain by a small peptide linker. Dulaglutide has been modified to render the molecule more stable against dipeptidylpeptidase-IV (DPP-IV) inactivation, increase the solubility of the peptide, reduce immunogenic potential, and increase the duration of its pharmacological activity. The pharmacokinetic (PK) half-life of dulaglutide is approximately 5 days, with less than 50% accumulation at steady state, supporting once-weekly dosing. The maximum dulaglutide plasma concentration ( $C_{max}$ ) was observed between 24 and 72 hours following subcutaneous administration.

In clinical trials completed to date, dulaglutide has exhibited the expected GLP-1 receptor agonist pharmacological effect on insulin secretion resulting in significant reductions in glycosylated hemoglobin (HbA1c). Dulaglutide administration in patients with type 2 diabetes has been associated with reductions in body weight. No episodes of severe hypoglycemia have been reported in completed studies. The most common adverse events (AEs) reported in patients administered dulaglutide are those related to the gastrointestinal organ class, including nausea and vomiting. Other AEs that have been rarely reported in trials of dulaglutide include pancreatitis and medullary thyroid cancer (MTC); whether or not these are due to exposure to the analog remains unknown. More detailed information about the known benefits and risks of dulaglutide may be found in the Investigator's Brochure (IB).

The purpose of this trial is to determine whether a once-weekly administration of dulaglutide compared to placebo reduces major adverse CV events, when added to the existing antihyperglycemic regimen of patients with type 2 diabetes who are at high risk for CV events. In addition, it will also assess the effect of the compound on other serious outcomes.

This study will be executed in compliance with the protocol, International Conference on Harmonization (ICH) guideline on good clinical practice (GCP), and applicable regulatory requirements.

## 6. Objectives

### 6.1. Primary Objective

The primary objective is to test the hypothesis that a once-weekly injection of 1.5-mg dulaglutide reduces the occurrence of the composite primary endpoint of death from cardiovascular (CV) causes, nonfatal myocardial infarction (MI), or nonfatal stroke when added to glucose-lowering regimen of patients with type 2 diabetes, compared to the addition of a once-weekly placebo injection.

### 6.2. Secondary Objectives

#### 6.2.1. Efficacy Objectives

The secondary efficacy objectives are to assess the effects of add-on therapy with 1.5-mg dulaglutide compared to placebo on the occurrence of:

- the composite microvascular endpoint of diabetic retinopathy requiring laser therapy, vitrectomy, or anti-vascular endothelial growth factor (anti-VEGF) therapy; development of clinical proteinuria, a 30% decline in estimated glomerular filtration rate (eGFR), or need for chronic renal replacement therapy
- hospitalization for unstable angina
- each component of the composite primary endpoint
- all-cause mortality
- heart failure (HF) requiring hospitalization or an urgent HF visit

#### 6.2.2. Prespecified Safety Objectives (AEs of Special Interest)

The prespecified safety objectives are to assess the effects of add-on therapy with 1.5-mg dulaglutide compared to placebo on the incidence of:

- acute pancreatitis
- serious gastrointestinal events
- any cancer (excluding basal or squamous cell skin cancer) and specific categories of
  - pancreatic cancer
  - medullary thyroid carcinoma (MTC) and C-cell hyperplasia
  - thyroid carcinomas
- severe hypoglycemia
- immune mediated reactions including serious allergic and hypersensitivity reactions
- serious hepatic events

- clinically significant supraventricular arrhythmias and cardiovascular conduction disorders
- serious renal events
- discontinuation of study drug for any reason

### **6.3. Additional Objectives**

[figure not shown]
The additional objectives are to assess the effects of add-on therapy with 1.5-mg dulaglutide compared to placebo on the following:

- hemoglobin A1c (HbA1c) levels
- weight
- waist/hip ratio
- the composite endpoint of death from CV causes, nonfatal MI, nonfatal stroke, or hospitalization for unstable angina
- coronary, carotid, or peripheral revascularizations, individually and compositely
- any hospitalization
- cognitive function as measured by the Montreal Cognitive Assessment (MoCA) and the Digit Symbol Substitution Test (DSST)
- erectile function using the International Index of Erectile Function Questionnaire (IIEF)
- any fracture
- development of cholelithiasis

## 7. Investigational Plan

### 7.1. Summary of Study Design

The REWIND trial is a Phase 3, multicenter, international, randomized, double-blind, placebo-controlled, parallel-group trial.

Study drug should be dispensed every 3 months. At the investigator's discretion, and after confirming sufficient non-expiring study drug is available onsite, a 6-month supply of study drug may be dispensed to maintain a patient's compliance with study drug.

Abbreviation: SOC = standard of care for type 2 diabetes management.

#### Figure GBDJ.1. REWIND trial design.

This study will assess the effect of once-weekly dulaglutide compared to placebo on major adverse CV events in patients with type 2 diabetes when added to their existing antihyperglycemic regimen. Patients 50 years of age or older who have type 2 diabetes treated with various antihyperglycemic regimens; have an HbA1c value  $\leq 9.5\%$  at screening; and have either established CV disease, documented subclinical CV disease, or multiple CV risk factors will be eligible to participate in this trial. All eligible patients will participate in a single-blind placebo run-in period. Patients who are adherent to study drug during the run-in period will be randomized in a 1:1 ratio to either 1.5-mg dulaglutide or placebo, injected subcutaneously once weekly (Figure GBDJ.1). After randomization, patients will be followed for CV outcomes and other measures at 2 weeks, 3 months, 6 months, and then followed at approximately 6 months thereafter. Management of glycemic control will be at the discretion of the study investigator and informed by current guidelines and routine patient management (Section 9.5.2). Either the study investigator or the patient's usual physician(s) will manage other CV risk factors and comorbid conditions (depending on local arrangements). The primary analysis of this study

is an intent-to-treat analysis; therefore, every randomized patient will be followed until death or study end regardless of adherence to study drug.

Approximately 9600 patients will be enrolled at approximately 480 sites globally and randomized to 1 of 2 treatment groups: 1.5-mg dulaglutide or placebo. Patients will be followed until approximately 1200 patients experience a primary endpoint event, centrally adjudicated as such. This is projected to occur after a minimum of 5.6 years and an average of approximately 6.5 years of follow-up on all patients, unless the trial is stopped early on the basis of an independent data monitoring committee (IDMC) safety review or the interim analysis.

Section 10 contains a discussion of specific study measures. Details regarding the study procedures at each visit are presented in the Study Schedule [Attachment 1](#)). A treatment duration of approximately 84 months (Visit 19) is planned but, if required, additional visits may occur beyond 84 months. These additional follow-up visits will occur in 6-month intervals (semiannually and annually). Activities for these visits will alternate between schedules for the Extended Follow-Up Visit a (EVA) for semiannual visits and the Extended Follow-Up Visit b (EVb) for annual visits ([Attachment 1](#)). Study drug dispensing will occur at every scheduled clinic visit ([Attachment 1](#)) except for Visit 4 and the Final Visit. Additional study drug-dispensing visits should occur at 3-month intervals between scheduled clinic visits ([Attachment 2](#)). At the investigator's discretion, and after confirming sufficient non-expiring study drug is available onsite, a 6-month supply of study drug may be dispensed to maintain a patient's compliance with study drug.

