## 2. Synopsis

### Study Rationale

Dulaglutide (LY2189265) is a glucagon-like peptide-1 (GLP-1) receptor agonist administered as a once-weekly subcutaneous injection to improve glycemic control in patients with type 2 diabetes mellitus. Dulaglutide has received regulatory approval in some countries and is under review in other countries.

Data from clinical trials have shown that dulaglutide reduces glycosylated hemoglobin (HbA1c), fasting and postprandial blood glucose, and body weight, and GLP-1 receptor agonists generally improve a variety of risk factors for cardiovascular (CV) disease. However, whether GLP-1 receptor agonists in general or dulaglutide in particular reduces CV outcomes is unknown. The purpose of this trial is therefore to assess the effect of once-weekly administration of dulaglutide compared to placebo on major adverse CV events when added to the existing antihyperglycemic regimen of patients with type 2 diabetes who are at high risk for CV events. Other serious outcomes will be assessed, including the effect of dulaglutide on thyroid C-cell function and the incidence of pancreatitis.

Name of Investigational Product: Dulaglutide (LY2189265)	
Title of Study: The Effect of Dulaglutide on Major Cardiovascular Events in Patients with Type 2 Diabetes: Researching Cardiovascular Events with a Weekly INcretin in Diabetes (REWIND)	
Approximate Number of Planned Patients/Subjects: Entered: 16,000 Enrolled/Randomized: 9600 Completed: 9500	Phase of Development: 3
Length of Study: This is an event-driven study and will complete when approximately 1200 patients experience a primary endpoint event, adjudicated as such. The estimated follow-up duration will depend on the observed cardiovascular (CV) event rate. Planned first patient visit: June 2011                      Planned last patient visit: Second Quarter 2019	

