Treatment period: Visits will continue until a sufficient number of primary endpoint events, adjudicated as such, have occurred. The estimated average follow-up duration is approximately 6.5 years.

**Reference Therapy, Dose, and Mode of Administration:** Placebo, administered subcutaneously once weekly

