## 7.3. Discussion of Design and Control

The objective of this trial is to determine whether the addition of the once -weekly GLP-1 receptor agonist dulaglutide to the diabetes regimen of patients with type 2 diabetes and high CV risk reduces major adverse CV and other serious outcomes. This is a multicenter, international, randomized, double-blind, placebo-controlled trial that will recruit patients 50 years of age or older with type 2 diabetes treated with various antihyperglycemic regimens who have either known clinical or subclinical CV disease or multiple CV risk factors.

A single-blind placebo run-in period will test a prospective patient's behavior and willingness to inject study drug on a weekly basis, given that patients will be expected to inject study therapy once weekly for 5 or more years. In this intent-to-treat study, adherence will be critical to assessing the impact of study drug on the natural progression of this chronic illness. Failure to comply with treatment also may have a profound impact on study power. The run-in period should provide a useful assessment of overall adherence to study drug injections.

Approximately 9600 patients will be enrolled and randomized to 1 of 2 treatment groups: 1.5-mg dulaglutide or placebo. Patients will be followed until approximately 1200 patients experience a primary endpoint event, centrally adjudicated as such. This is projected to occur after an average of approximately 6.5 years of follow-up on all patients, unless the trial is stopped early following an IDMC safety review or an interim analysis. Maximum duration of follow-up is dependent upon the primary endpoint event rate. Patients will be followed at approximately 6-month intervals. Management of glycemic control will be at the discretion of the study investigator and will be informed by current guidelines and/or local standards of medical care. The management of blood pressure, lipids, other CV risk factors and comorbid conditions will be at the discretion of the study investigator or the patient's usual physician(s), as informed by current guidelines and the patient's clinical state.

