Superiority will be assessed by the reduction in risk of the primary composite endpoint of death from CV causes, nonfatal MI, or nonfatal stroke. This same primary efficacy endpoint was used in the ACCORD study (ACCORD 2008) and in many other studies in CV research (ADVANCE 2008; Duckworth et al. 2009). The CV event rate is assumed to be about 2% annually, based on recently completed trials in patients with type 2 diabetes (ACCORD 2008; ADVANCE 2008). Given this, in order to assess long-term clinical CV outcomes, patients are expected to be followed for between 5 and 8 years; however, the actual duration of the study will depend on the observed CV event rate and time to accrue the number of anticipated primary CV events (approximately 1200). As the primary analysis of this study is an intent-to-treat analysis, every randomized patient will be followed until death or study end. Every attempt will be made to encourage all patients to come for their study visits. The long duration of this trial will also enable a robust assessment of dulaglutide on other measures, including its effects on thyroid C-cell function, microvascular complications, and the incidence of pancreatitis.

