## 12. Sample Size and Statistical Methods

### 12.1. Determination of Sample Size

A sample size of approximately 9600 patients is required to show superiority of dulaglutide over placebo (with 90% power), as was calculated using nQuery Advisor® Version 7.0. This software provides sample size estimates for tests based on exponential survival, accrual period, and dropouts. The sample size and other trial characteristics, such as interim analysis power, were also assessed through trial simulation. Trial assumptions were based on information from the scientific leadership of the study and a review of the relevant literature. For sample size determination the following assumptions were used: (1) two-sided significance level of 0.05; (2) 90% power for the primary endpoint; (3) patient accrual over 3 years; (4) annual placebo group event rate of 2.0% for the primary endpoint; (5) maximum duration of follow-up of 8 years; (6) a detectable hazard ratio of 0.82 between dulaglutide and placebo in terms of the primary endpoint; and (7) annual dropout rate of 0.15%.

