### **12.2.2. Trial Design**

There will be 1 interim analysis and 1 final analysis. The interim analysis will be performed when approximately 61% (730 events) of the positively adjudicated primary endpoint events have occurred. The final analysis will be performed at 100% (approximately 1200) of the positively adjudicated primary endpoint events, if the study is not stopped early. At the interim analysis timepoint ([Figure GBDJ.2](#)), superiority will be tested first; if successful, the trial may stop and superiority will be declared. Otherwise, the trial will continue to the end, where, at 1200 events, superiority will be tested followed by noninferiority. The interim and final analyses will be performed on unblinded study data. The interim analysis results and these decision rules are used by the IDMC as guidelines. If the interim analysis shows clear benefit of dulaglutide over placebo for the primary endpoint, the IDMC may recommend early termination of the study. Alternatively, if the boundaries are crossed at the interim analysis, the IDMC may still recommend the trial continue and not stop for early efficacy. At anytime during the trial, the IDMC could recommend stopping the trial for safety reasons. The alpha used across the analyses will be monitored by an O'Brien-Fleming spending function (O'Brien and Fleming 1979; Jennison and Turnbull 2000), (eg, with 730 events at the interim, 2-sided alpha = 0.0081). The alpha used at the final analysis will be adjusted to maintain the overall type I error control at a 2-sided significance level of 0.05. This will be accomplished using EAST software to calculate the alpha level for the final analysis considering the actual amount of information at the interim analysis (eg, with 1200 events at the final analysis, 2-sided alpha = 0.0475; overall power = 92.8%). If the true hazard ratio is as high as 0.85, this sample size would provide at least 80% overall power to show superiority. At the final analysis, superiority will be tested. The adjusted 95% CI for the hazard ratio will be calculated.

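### Does the projected follow-up for 1200 events contradict the placebo rate and hazard ratios that the plan states?

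*Protocol*

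**What the plan says.** Protocol 7.1 ties the 1200-event target to a duration: "This is projected to occur after a minimum of 5.6 years and an average of approximately 6.5 years of follow-up on all patients". The Synopsis repeats the average ("The estimated average follow-up duration is approximately 6.5 years") and dates the end ("Planned last patient visit: Second Quarter 2019"). Section 7.3 gives the same average ("This is projected to occur after an average of approximately 6.5 years of follow-up on all patients").

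The event rate appears in two forms:

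- Section 7.3 names no arm: "The CV event rate is assumed to be about 2% annually". It adds that "patients are expected to be followed for between 5 and 8 years" and that the actual length depends on the observed rate.
- Section 12.1, like SAP 4.1, names the arm: "annual placebo group event rate of 2.0% for the primary endpoint". The companion inputs are a hazard ratio of 0.82, 3 years of accrual, 8 years maximum follow-up and 0.15% dropout per year.

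Section 12.2.2 adds a less favourable effect: "If the true hazard ratio is as high as 0.85, this sample size would provide at least 80% overall power to show superiority".

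Protocol Attachment 5 explains the current 5.6-year figure. Enrolment took 2.1 years, and a 2% annual event rate then puts 1200 events in the second quarter of 2019. It names no arm and uses no hazard ratio for the date.

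**The concern.** A reader who wants to check the timeline looks for arm-level rates and finds one set: placebo 2.0%, with a hazard ratio of 0.82 or 0.85. If dulaglutide works as assumed, the overall rate is below 2%, and the events arrive more slowly than Section 7.1 says.

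On that reading the shortfall at the planned close is about 85 to 112 events. The last visit would slip by more than half a year, the longest follow-up would pass the 8 years in Section 7.3, and more patients would go beyond Visit 19 (84 months). Sites and supply planners would be working from dates that are too early. The 2% would also be doing two jobs, as the placebo rate in Section 12.1 and the all-patient rate behind Section 7.1, without the plan saying so.

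**Working it through.** **Inputs.** N = 9600, 1:1, target 1200, minimum F = 5.6 years (Protocol 7.1); accrual A = 2.1 years (Attachment 5); dropout d = 0.0015 per year, placebo rate 2.0%, HR 0.82 (12.1, SAP 4.1); HR 0.85 (12.2.2). Uniform entry and exponential event times are assumptions. The 2% is taken either as a hazard (λ = 0.02) or as an annual probability (λ = −ln 0.98 = 0.020203).

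**Formula.** For n patients with hazard λ, and m = λ + d:

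`events = n × (λ/m) × [1 − (exp(−mF) − exp(−m(F+A))) / (mA)]`

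**1. The projection on its own basis: 2% in all 9600 patients.** With λ = 0.020203, m = 0.021703:

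- exp(−5.6m) = 0.88556; exp(−7.7m) = 0.84611; mA = 0.045576
- (0.88556 − 0.84611)/0.045576 = 0.8657
- events = 9600 × 0.93088 × (1 − 0.8657) ≈ 1200

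With λ = 0.02 the result is 1189. Solving for 1200 events gives a minimum of 5.60 years (probability) or 5.67 years (hazard). The stated minimum reproduces.

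Mean time from entry to close is 5.6 + 2.1/2 = 6.65 years. Mean time to first event, dropout or close is (1200/9600)/0.020203 = 6.19 years. The stated average of about 6.5 lies between these two.

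**2. The same calendar with 2.0% as the placebo rate and the design effect.** 4800 patients per arm:

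| HR | Placebo events | Dulaglutide events | Total |
|---|---|---|---|
| 0.82 | 595 to 600 | 493 to 498 | 1088 to 1098 |
| 0.85 | 595 to 600 | 510 to 515 | 1105 to 1115 |

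The shortfall is 1200 − 1115 = 85 to 1200 − 1088 = 112 events, or 7% to 9%.

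**3. Follow-up needed for 1200 on that second reading.**

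| HR | Minimum (y) | Average to close (y) | Longest (y) | Delay (months) |
|---|---|---|---|---|
| 0.85 | 6.14 to 6.22 | 7.19 to 7.27 | 8.24 to 8.32 | 6.5 to 7.4 |
| 0.82 | 6.26 to 6.34 | 7.31 to 7.39 | 8.36 to 8.44 | 8.0 to 8.9 |

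The delay is (minimum − 5.6) × 12. The stated calendar has a longest follow-up of 5.6 + 2.1 = 7.7 years.

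**4. What a 2% overall rate implies.** To reach 1200 events at 5.6 years, the placebo hazard would be 2.18% (HR 0.85) or 2.22% (HR 0.82) per year. With no treatment effect, a placebo rate of 2.0% is itself the overall rate and gives the 1189 to 1200 of step 1.

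**5. The initial sizing.** Placebo 2.0%, HR 0.82, A = 3, F = 8 − 3 = 5 gives 1064 to 1074 events, against 1067 in SAP 4.1. So 2.0% really is the placebo rate there, and that calculation is sound.

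**6. Power at the event target.** With O'Brien-Fleming-type spending at 730/1200, the two-sided alpha is 0.0081 at the interim and 0.0474 at the end (stated: 0.0475). Overall power is 92.8% at HR 0.82 and 80.0% at HR 0.85, as stated. None of this uses calendar time.

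**The case for a change.** The strongest case for a change is that the arm-level shortfall is real and robust. Accrual shape cannot remove it: even if every patient had exactly 6.5 years, placebo 2.0% would give only about 1081 (HR 0.82) to 1098 (HR 0.85) events without dropout. Nor does it depend on Attachment 5. Section 7.1's own 5.6 and 6.5 years imply a uniform accrual span of 2 × (6.5 − 5.6) = 1.8 years, and that gives 1065 to 1092. An overall rate of 2% with the design effect implies a placebo rate near 2.2%, which is not the figure printed in Section 12.1. The plan does not say which population the 2% describes.

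All of that arithmetic stands, but it does not show that the projection is wrong. It tests a forecast made after enrolment ended against inputs that the forecast does not cite; SAP 4.1 itself presents those inputs as belonging to the initial powering. An unlabelled rate used to predict a count over both arms reads most naturally as an overall rate, and blinded study staff can observe only an overall rate (Protocol 9.7). This is inference, since no passage calls the rate pooled. Still, nothing in the text favours the placebo reading, and a calendar forecast need not assume the hoped-for effect.

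What stands is the missing label.

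**Conclusion.** The projection is not in error. On its stated basis it gives 1189 to 1200 events at the planned close. It misses only if the placebo rate and hazard ratio from the sizing paragraph are brought in, which gives 1088 to 1115 events and a close 6.5 to 8.9 months later. Restating the durations on that second basis would replace a forecast that reproduces with one built on inputs it never cited.

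The gap is one missing word about which patients the 2% describes, and filling it would gain nothing. Close-out follows the adjudicated count (Protocol 7.1.5). The Synopsis and Section 7.3 already make duration depend on the observed rate, and Section 7.1 provides visits beyond 84 months. If events come more slowly, the trial simply runs longer under rules already written. The event target, alpha, power, analysis and conclusions stay the same on either reading.

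This rests on uniform accrual, constant hazards and the stated dropout. Reading the 2% as an overall rate is an inference from the fit and the context.
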